1.1.5. Safety analysis

- Safety endpoints and adverse effects during 3, 6 and 12 months post-procedure compared between the 2 groups (RDN-Treatment group vs. Sham group).
- Listing of AE and ADE in original term provided for each patient (Solo-Population)
Listing of SAE, AESI, SADE in original term provided for each patient
Comparison of number / percentages of SAE, AE, AESI, escape rate between the 2 groups (RDN-Treatment group vs. Sham group)
- Increase of serum creatinine / eGFR (calculated based on CKD-epi) between visit 3a (week 0) and visit 3b, and visit 3a and visit 4 (week +3) between the 2 groups (RDN-Treatment group vs. Sham group) and in each group separately

Following events will be presented at all-time points post-procedure comparing 2 groups

All-cause mortality
New onset ESRD (eGFR<15 mL/min/m ² or need for renal replacement therapy)
Significant embolic event resulting in end-organ damage
Renal artery perforation or dissection requiring an invasive intervention
Major vascular complications requiring surgical repair, interventional procedure, thrombin injection, or blood transfusion
Hospitalization for hypertensive or hypotensive crisis
Hospitalization for major cardiovascular or hemodynamic related events
New onset stroke
New onset myocardial infarction
Suspicion of new onset renal artery stenosis by renal duplex ultrasound

Following AESIs will be presented as a table at all time points post-procedure comparing 2 groups

- All-cause mortality
- Hypertensive emergency resulting in hospitalization
- Hypotensive emergency resulting in hospitalization
- Hospitalization for heart failure
- Stroke, transient ischemic attack, cerebrovascular accident
- Acute myocardial infarction (STEMI/non-STEMI)
- Any coronary revascularization
- End stage renal disease, the need for permanent renal replacement therapy (i.e. the need for dialysis); doubling of plasma creatinine, eGFR <15ml/min/1.73m²
- Any renal artery complication requiring intervention (e.g. dissection; perforation)
- Major access site complications requiring intervention
- Significant embolic events resulting in end organ damage
- Procedure-related pain lasting for > 2 days
- Acute renal injury, defined as:

- Increase in serum/plasma creatinine to ≥ 1.5 times pre-procedure visit (week -1) or decrease of eGFR (derived from creatinine, CKD-epi) by 25% known to have occurred during 7 days post procedure or
- Urine volume < 0.5 ml/kg/h for 6 hours

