- Significant ($> 50\%$) and severe ($> 70\%$) new onset renal stenosis as diagnosed by renal angiogram or CTA/MRA
- Need for renal artery angioplasty or stenting

In addition, these AESIs will also be reported as 1-month post-procedure event rates:

- Any renal artery complication requiring intervention (e.g. dissection; perforation)
- Major access site complications requiring intervention
- Significant embolic events resulting in end organ damage
- Procedure-related pain lasting for > 2 days
- Acute renal injury, defined as:
 - increase in serum/plasma creatinine to ≥ 1.5 times pre-procedure visit (week -1) or decrease of eGFR (derived from creatinine, CKD-epi) by 25% known to have occurred during 7 days post procedure or,
 - Urine volume < 0.5 ml/kg/h for 6 hours

Following major combined safety endpoint (incidence of any major adverse events (MAE) through the FU) at all time points post-procedure comparing 2 groups

- All-cause mortality
- eGFR < 15 ml/min/1.73m² or permanent need for renal replacement therapy
- Hospitalization for hypertensive crisis defined by office (attended) BP $\geq 180/110$ mmHg with clinical symptoms
- Clinical manifestation of hypertension associated target organ damage requiring hospitalization
- New renal artery stenosis $> 75\%$ as assessed by computer tomography (CT)/magnetic resonance angiography (MRA) or diagnosed/confirmed by renal angiogram
- Individual components of the combined endpoint above

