1.2. Design of the Trial

RDN-CKD Study is a prospective, randomized (1:1, central randomization), double-blind (unblinded interventionalist and blinded study team at each center), sham controlled, multicenter feasibility study. All centers have participated at least in one of the sham-controlled trials in primary hypertension thereby having established an unblinded and a blinded team.

The RDN-CKD Study has been conducted at 5 clinical investigational sites, which are the University Hospitals in Erlangen, Homburg/Saar, Düsseldorf, Berlin and Nürnberg.

We aimed to include 80 patients with CKD stages 3a or 3b (according to the currently used estimation formulas [MDRD, CKD-EPI] and uncontrolled hypertension in the RDN-CKD study. This number of patients could not be achieved due to diverse reasons (pandemic, low recruitment). Therefore the recruitment got stopped by 31.12.2022.

If the patient fulfils inclusion criteria and in the absence of exclusion criteria at visit 1, the patient has been enrolled into the trial, and the study visits were scheduled. All subjects have their office BP measured, a limited medical history review, physical exam and current medication review and a safety laboratory evaluation. Furthermore, an ABP measurement was conducted. Visit 2 serves a FU in the run-in phase. All subjects were checked for medication adherence. A 24-h ambulatory BP measurement was conducted. Additionally, all subjects had their office BP measured, physical exam and current medication review and a safety laboratory evaluation. Once a subject has met all the screening criteria for the study the visit was scheduled for the renal angiogram and RDN/Sham procedure. Subjects of child bearing potential must have a documented negative pregnancy test dated within a maximum of 7 days prior to the procedure.

Randomization occurred following the diagnostic renal angiogram. Only randomized patients counted towards the enrollment ceiling. FU Visits took place 3 weeks, 6 weeks, 12 weeks, 19 weeks, 26 weeks, 39 weeks, 52 weeks post procedure. All baseline measurements were repeated 12 weeks, 26 weeks and 52 weeks post-procedure. Due to early recruitment stop of the study certain number of patients had only FU visits till 26 weeks post procedure.

Escape Criteria

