1.3. Trial Flow Sheet

Enrollment of subjects occurred at the clinical sites only after the appropriate local study approvals, “Approval to Enroll” documentation from the Sponsor and written informed consent from subjects have been obtained.

Visit #	V1	V2	V3	V4	V5	V6	V7	V8 ⁷	V9	V10
Week	-4	-1	0	3	6	12	19	26	39	52
Informed consent	X									
Inclusion/exclusion criteria	X									
Medical history	X									
RDN/Sham Procedure			X							
Physical exam	X	X	X	X	X	X	X	X	X	X
24-h ABP measurement ¹	X	X				X		X		X
Office (attended) BP ²	X	X	X	X	X	X	X	X	X	X
Safety and efficacy lab	X	X	X	X	X	X	X	X	X	X
AEs/ADEs	X	X	X	X	X	X	X	X	X	X
UACR ³ , eGFR, Cystatin C	X	X				X		X		X
Urinary toxicological analyses ⁴		X				X		X		X
Body fluid composition		X						X		X
MRA of Renal Arteries ⁵		X								
Duplex ultrasound ⁶		X								X
Medication review	X	X	X	X	X	X	X	X	X	X

Visit schedule (# all visits can be scheduled +/-5days)

- 24-h ambulatory BP measurements will be conducted by mobilograph (IEM, Aachen) allowing also the assessment of central systolic BP in addition to brachial BP readings.
- Office (attended) BP according to ESH guidelines with automated oscillometric device while nurse/physician is in the room (attended visits).
- UACR – albumin/creatinine ratio.
- To assess adherence to prescribed medication
- MRA has only to be performed if no images (previous MRI, previous CT, previous angiogram) of anatomy of renal artery supply is available
- If the last duplex sonography examination displays signs of renal artery stenosis or is not fully evaluable according to the investigator’s discretion, an angiogram needs to be performed to rule out or diagnose any renal artery abnormality which can be compared with the angiogram performed at baseline.
- Patients who will not have 12 months follow up visit until June 2023 but thereafter will have a shorter follow up period of 6 months only and unblinding will take place after all data of the 6 months FU visit have been entered and secured in the database (the rationale is that the primary objective is change in blood pressure after 6 months!

2. Outcome Measures and Target Parameters

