2.2. Safety

All adverse events were collected, coded and reported, for the duration of the study according to the definitions of “Clinical investigation of medical devices for human subjects -Good clinical practice” ISO: 14155: 2011.

The occurrence rate for all the clinical events defined below [referred to as adverse events of special interests (AESIS)] will be calculated for each cohort, characterized by the Data Safety Monitoring Board (DSMB) and compared between and within arms (where applicable) for the duration of the study. In addition, specific events within this list will also be reported as event rates within specific time frames post procedure.

The assessment of safety was based primarily on the frequency of serious adverse device effects (SADEs) serious adverse events (SAEs), adverse device effects (ADEs), adverse events(AEs) and laboratory abnormalities classified by Investigators as related to the RDN and confirmed by the DSMB. Occurrence and frequency of SADEs and ADEs and AE(s) and SAE(s) was summarized by treatment group at baseline, last visit and by changes from baseline to last visit for laboratory values. Other safety data were summarized as appropriate.

The RDN-CKD Study DSMB is comprised of independent experts in hypertension, interventional radiology or cardiology and biostatistics. The DSMB was responsible for the oversight, review of all relevant SAEs including but not limited to:

- All unanticipated events

- All events pre-specified as part of the overall safety assessment
- All device- or procedure-related events (ADEs and SADEs)
- Deaths

During the course of the study, the DSMB reviewed accumulating safety data blinded to subject randomization in order to monitor the incidence of protocol-defined events and other trends that would warrant modification or termination of the study. Responsibilities, qualifications, membership, and committee procedures were outlined in the DSMB Charter.

All safety aspects mentioned in chapter 1.1.5 will be listed and compared between RDN and sham group.

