- Resolved
- Resolved with sequelae
- Ongoing
- Death

Recording and Reporting of Adverse Events

The period of observation for AEs extends from Study Screening/Baseline Eligibility Visit 1 (Week -4) until Visit 10 (Week +52). New AEs reported to the investigator during the observational period, after the study procedure must be documented, treated, and followed up like all other AEs.

AEs will not be followed up after the final investigation visit which is scheduled 12 months after the treatment with the investigational medical device.

Underlying diseases/pre-existing conditions that do not worsen during the course of the investigation are not reportable as AEs. To determine whether a condition has worsened, it is compared to the condition of the subject at baseline.

Elective treatments planned before screening and which are documented in the subject's source data are usually not regarded as AEs.

Data pertaining to AEs will be collected during each investigation visit based through the investigators inquiry or discovered in the course of examinations done during the visit. The investigators will assess and record any AE in detail in the subject file and on the CRF AE report form.

The following information were recorded:

- AE diagnosis or main symptom.
- Date of event onset.
- Severity
- Investigational medical device (blinded)
- Causal relationship (causal related, probably related, possibly related, unlikely related, not related).
- Serious (yes or no).
- Patient outcome
- Action taken /treatment.
- AE falling under the definition of an AESI (yes or no)
- AE leading to discontinuation of the investigation (yes or no)
- AE due to a device deficiency (yes/no)
- Date of event resolution

After completion of all scheduled visit assessments the investigator must document any AEs arising from these assessments. In case of an SAE, the investigator must also complete an SAE report form.

Recording and Reporting of Serious Adverse Events

All SAEs that occur during the investigation period, whether considered to be related to the investigational medical device/procedures or not, were reported by the investigator to the Sponsor within 24 hours of knowledge.

SAE report forms are provided in the ISF. Completed reports were signed by an investigator and transferred by fax to:

Medical Device Vigilance Office
Center for Clinical Studies (CCS Erlangen)
Universitätsklinikum Erlangen
[name]

[name]
[contact]
email: [contact]

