2.9.5.1. Adverse Events

Frequency tables for the preferred terms will be compiled, based on patients experiencing an AE and based on the number of AEs. The AE will also be analysed with regard to system organ class. They will be displayed with regard to severity and relationship to study drug. All AEs will be listed.

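### Safety percentages at 12 months and over the whole follow-up are too low for late events, because patients stopped at week 26 stay in the denominator

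*SAP*

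**What the plan says.** **How safety is summarised.** Section 1.1.5 calls for "Comparison of number / percentages of SAE, AE, AESI, escape rate between the 2 groups" and for "Safety endpoints and adverse effects during 3, 6 and 12 months post-procedure compared between the 2 groups". Its combined safety endpoint is the "incidence of any major adverse events (MAE) through the FU", shown at all time points. Section 2.9.5.1 adds: "Frequency tables for the preferred terms will be compiled, based on patients experiencing an AE and based on the number of AEs". Section 2.2 speaks of "The occurrence rate for all the clinical events defined below" per cohort but names no denominator. The only explicit short-window rates are the 1-month rates for five AESIs in section 1.1.5.

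**In whom.** Section 2.9.5 puts every safety analysis on the SAF population. Section 2.3 defines that population by informed consent alone.

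**For how long.** Section 1.2 states that a "certain number of patients had only FU visits till 26 weeks post procedure". The flow-sheet note in section 1.3 gives the rule: patients whose 12-month visit would fall after June 2023 "will have a shorter follow up period of 6 months only". Section 2.8 nevertheless lets the adverse event observation period run "until Visit 10 (Week +52"), with no exception for these patients.

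Nowhere does the SAP give an at-risk denominator, a censoring rule, a time-to-event estimate or person-time for safety.

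**The concern.** A percentage of patients with an event by 12 months estimates 12-month risk only if everyone in the denominator was observed for 12 months or had the event before observation ended. Here a group defined by calendar date was observed for half that time. Its members add a full unit to the denominator and nothing to the numerator after week 26.

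Verifying safety is a stated objective (section 1.1), so a 12-month figure for MAE, AESI or SAE that is too low errs in the reassuring direction. Counts of events have the same weakness, since they are not related to observation time.

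**Working it through.** The SAP states no event risk, no number truncated and no final sample size, so there is no figure of its own to reproduce. The size is shown under assumptions.

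**Inputs from the SAP.** 1:1 randomisation; 80 patients planned and not reached; recruitment stopped on 31.12.2022 (section 1.2). Follow-up is 26 or 52 weeks by a calendar rule (section 1.3). Patients whose procedure fell later than about mid-2022 are therefore the ones cut. Their share is not stated.

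**Assumed.** True 12-month risk p, constant hazard, share f of patients stopped at 6 months.

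**Formulas.**
- 6-month risk: p6 = 1 − √(1 − p)
- Crude 12-month percentage: (1 − f)·p + f·p6
- Relative shortfall: f·(p − p6)/p, that is, f times the share of 12-month first events falling in months 6 to 12

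**p = 20%.** p6 = 1 − √0.80 = 10.56%. The late share is (20 − 10.56)/20 = 0.472.

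| f | Crude 12-month percentage | Relative shortfall |
|---|---|---|
| 20% | 0.8 × 20 + 0.2 × 10.56 = 18.1% | 0.2 × 0.472 = 9% |
| 25% | 0.75 × 20 + 0.25 × 10.56 = 17.6% | 0.25 × 0.472 = 12% |
| 50% | 0.5 × 20 + 0.5 × 10.56 = 15.3% | 0.5 × 0.472 = 24% |

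**Other risks.** For p from 5% to 50% the relative shortfall is 4–5% at f = 10%, 10–12% at f = 25%, 21–25% at f = 50% and 31–37% at f = 75%. It depends mainly on f, little on p.

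**Other event timing.** If all events come early, the late share is 0 and there is no shortfall. If an event is found only at week 52, the late share is 1 and the shortfall is f itself. Duplex-suspected renal artery stenosis, a listed event in section 1.1.5, is close to the second case: the flow sheet in section 1.3 schedules duplex at week −1 and week 52 only, so a patient stopped at week 26 has no scheduled post-procedure scan.

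**Between arms.** The cut follows the calendar, so the truncated share is equal between arms in expectation. The chance imbalance is hypergeometric. With an assumed 20 of 50 patients truncated and 25 per arm, the shares differ by 24 points or more with probability about 0.15. A difference of 20 points or more has probability 0.27 (f = 25%) to 0.34 (f = 50%) with 40 patients, and 0.07 to 0.12 with 80. Its effect at p = 20%, equal hazards and truncated shares of 40% and 60%:
- 0.6 × 20 + 0.4 × 10.56 = 16.2%
- 0.4 × 20 + 0.6 × 10.56 = 14.3%

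This is a spurious difference of 1.9 points (ratio 1.13). The standard error of a difference between two arms of 25 at 20% risk is √(2 × 0.2 × 0.8/25) = 11.3 points, so the artefact is small beside sampling error.

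**Does the remedy work?** Everyone informs the first 6 months (10.56%), and those followed further give a conditional risk of 10.56% for months 6 to 12. Kaplan-Meier combines them: 1 − 0.8944² = 20.0%. In a simulation with f = 25% and 50%, Kaplan-Meier and the person-time rate converted to 12-month risk both returned 20.0%.

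**The case against.** **The denominator is inferred.** Section 1.1.5 does not name one. SAF cannot be the literal per-arm denominator, because it includes consented patients who were never randomised, and section 2.9.3 confines untreated patients to listings. Using only patients with 12-month follow-up would remove the shortfall. This is fair as far as it goes. But the SAP assigns SAF to all safety analyses, and the one restriction it makes concerns treatment, not length of follow-up. Followed as written, patients stopped at week 26 remain in the 12-month percentage.

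**Much of the safety picture is untouched.** This stands. The 1-, 3- and 6-month windows are not affected by the cut, nor are access-site complications, dissection or perforation at the procedure, procedural pain, or renal injury within 7 days. A reader might infer that all safety incidence is too low; the SAP does not support that.

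**The arms are not confounded with exposure.** This also stands. A reader might infer that unequal observation time biases the RDN-versus-sham comparison. The cut is a calendar rule under 1:1 randomisation and the SAP shows no imbalance. Chance imbalance is possible in a small trial, with the modest effect shown above.

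**The stakes are limited.** The trial is a feasibility study, section 2.4 makes the analysis exploratory and descriptive, and onset dates are recorded, so timing can be recovered. This lowers the urgency. It does not cure the figure, since a descriptive incidence is exactly what is affected.

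**Kaplan-Meier alone is not enough.** Correct: death competes with non-fatal events, and no estimator supplies a duplex scan that was not scheduled. The fix below allows for both.

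**Conclusion.** The point holds for the 12-month and whole-follow-up summaries of MAE, AESI and SAE, for events that can occur after week 26. The direction is certain wherever such events occur. The size is not known, because the SAP gives neither the truncated share nor the event timing. The range of 9% to 24% rests on an assumed 20% risk, constant hazard and 20% to 50% truncated. It illustrates the mechanism and should not be read as an estimate for this trial. Unequal exposure between arms through this cut is a chance risk only. This is a cheap improvement, not a threat to the trial's conclusions.

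**What to change.** In sections 1.1.5, 2.2 and 2.9.5 of the SAP:

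1. Make 6-month incidence in treated randomised patients the main safety comparison. All of them were scheduled to be followed that long.
2. For 12 months, replace crude percentages with Kaplan-Meier estimates for MAE and death, and with cumulative incidence treating death as a competing event for non-fatal AESI and SAE. Give 95% CIs and numbers at risk by arm, and censor at the end of each patient's follow-up.
3. Report AE and SAE counts per patient-year, with person-time by arm.
4. For duplex-suspected stenosis, use as denominator the patients who had a post-procedure duplex, and state their number by arm.
5. Reconcile the adverse event observation period in section 2.8 with the shortened follow-up in section 1.3.

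The cost is wording and standard analyses on dates already collected. The 12-month figures will be slightly higher and their confidence intervals wider.

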1.2. Design of the Trial

RDN-CKD Study is a prospective, randomized (1:1, central randomization), double-blind (unblinded interventionalist and blinded study team at each center), sham controlled, multicenter feasibility study. All centers have participated at least in one of the sham-controlled trials in primary hypertension thereby having established an unblinded and a blinded team.

The RDN-CKD Study has been conducted at 5 clinical investigational sites, which are the University Hospitals in Erlangen, Homburg/Saar, Düsseldorf, Berlin and Nürnberg.

We aimed to include 80 patients with CKD stages 3a or 3b (according to the currently used estimation formulas [MDRD, CKD-EPI] and uncontrolled hypertension in the RDN-CKD study. This number of patients could not be achieved due to diverse reasons (pandemic, low recruitment). Therefore the recruitment got stopped by 31.12.2022.

If the patient fulfils inclusion criteria and in the absence of exclusion criteria at visit 1, the patient has been enrolled into the trial, and the study visits were scheduled. All subjects have their office BP measured, a limited medical history review, physical exam and current medication review and a safety laboratory evaluation. Furthermore, an ABP measurement was conducted. Visit 2 serves a FU in the run-in phase. All subjects were checked for medication adherence. A 24-h ambulatory BP measurement was conducted. Additionally, all subjects had their office BP measured, physical exam and current medication review and a safety laboratory evaluation. Once a subject has met all the screening criteria for the study the visit was scheduled for the renal angiogram and RDN/Sham procedure. Subjects of child bearing potential must have a documented negative pregnancy test dated within a maximum of 7 days prior to the procedure.

Randomization occurred following the diagnostic renal angiogram. Only randomized patients counted towards the enrollment ceiling. FU Visits took place 3 weeks, 6 weeks, 12 weeks, 19 weeks, 26 weeks, 39 weeks, 52 weeks post procedure. All baseline measurements were repeated 12 weeks, 26 weeks and 52 weeks post-procedure. Due to early recruitment stop of the study certain number of patients had only FU visits till 26 weeks post procedure.

Escape Criteria

Enrolled subjects will be excluded if office BP exceeds $\geq 170/105$ mmHg confirmed by 7-day average of home blood pressure measurements \geq BP $> 160/100$ mmHg (excluding white coat effect) and confirmed by office BP $\geq 170/105$ mmHg at another study visit.

Unscheduled visit (UV)

In case subjects will be seen at additional times other than regular scheduled study visits, if deemed necessary by the Investigator, the following safety assessments will be performed: safety laboratory, urinalysis, vital signs, physical examination, AE assessment, checking concomitant medication.

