1.1.2. Secondary objectives

The secondary efficacy parameters of the study are (*between the 2 groups* - RDN-Treatment group vs. Sham group):

- Change in systolic 24-h ambulatory BP at 3 and 12 months post-procedure from pre-procedure (including P and B) compared between the 2 groups (RDN-Treatment group vs. Sham group).
- Change in diastolic 24-h ambulatory BP at 3, 6 and 12 months post-procedure from pre-procedure (including P and B) compared between the 2 groups (RDN-Treatment group vs. Sham group).
- Change in office systolic and diastolic BP at 3, 6 and 12 months post-procedure from pre-procedure (including P and B) compared between the 2 groups (RDN-Treatment group vs. Sham group).
- Change in home systolic and diastolic BP at 3, 6 and 12 months post-procedure from pre-procedure (including B only) compared between the 2 groups (RDN-Treatment group vs. Sham group).
- Responder rate in BP (systolic office BP ≥ 10 mmHg, or 24-h systolic ambulatory BP ≥ 5

mmHg) at 3, 6, and 12 months post-procedure from pre-procedure (including P and B) compared between the 2 groups (RDN-Treatment group vs. Sham group).

- Change in serum creatinine, cystatin C at all time points from pre-procedure (pre-procedure visit (week -1) value and screening visit (week -4)) compared between the 2 groups (RDN-Treatment group vs. Sham group).
- Change in eGFR (calculated based on CKD-epi formula) derived from serum creatinine at all time points from pre-procedure (pre-procedure visit (week -1) value and screening visit (week -4)) compared between the 2 groups (RDN-Treatment group vs. Sham group). [1]
- Change in eGFR derived from cystatin C at all time points from pre-procedure (pre-procedure visit (week -1) value and screening visit (week -4)) compared between the 2 groups (RDN-Treatment group vs. Sham group). [2, 3]
- Change in eGFR derived from creatinine/Cystatin-C formula at all time points from pre-procedure (pre-procedure visit (week -1) value and screening visit (week -4)) compared between the 2 groups (RDN-Treatment group vs. Sham group) [3]
- Change of the slope of eGFR (derived from creatinine; CKD-epi formula) after half year and one year post-procedure from pre-procedure (pre-procedure visit (week -1) value and screening visit (week -4) eGFR values) compared between the 2 groups (RDN-Treatment group vs. Sham group).

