2.4. Analyses

Statistical analyses will be based on the basis of international guidelines (CPMP/ICH/363/96:E9). Due to the early stop of the study, only an exploratory and descriptive analysis takes place. Statistical methods used to compare groups for primary and secondary outcomes:

Efficacy: Change of systolic 24-h ambulatory BP at 6 months post-procedure (primary efficacy endpoint) compared between the RDN and sham group will be analyzed in a linear mixed model including the covariates that were significantly different between the groups at baseline. All secondary (see 1.1.2) and observational endpoints (1.1.3 and 1.1.4) are analyzed also via a modelling approach adjusting for potential imbalances in baseline characteristics. The type I error for the analysis of the primary endpoint is set at 5% (two-sided), all analyses of secondary endpoints have an exploratory character avoiding multiplicity issues in this trial.

In addition, a win ratio analysis will be conducted, with the criteria 24h ambulatory systolic BP change > 5 mmHg, office systolic BP change > 10 mmHg, and decrease of medication as defined by following 3 parameters (number of antihypertensive drugs, drug burden index and antihypertensive load index).

Analysis will be performed for the following populations:

1. Primary analysis is based on *the intention-to-treat* (ITT) population consisting of all randomized study subjects that are all either RDN treated or sham treated.
2. A secondary analysis will be done with a *modified ITT* population (mITT) in which participants with adherence violations will be excluded (sensitivity analyses).
3. A secondary analysis will be done with the *per protocol population* (PPP) in which study subjects with predefined protocol deviations (defined prior to unblinding of the data) are excluded.
4. A secondary analysis will be done with the modified *per protocol population* (mPPP) in which study subjects of the PPP with adherence violation are excluded.
5. A secondary analysis will be done with the safety population (SAF) in which all study subjects signing informed consent are included.

6. A secondary analysis will be done with those patients that are investigated by the Erlanger and Nürnberger center (CRC staff), with a total of N=20 randomized patients (Bavarian cohort)

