2.9. General Analysis

2.9.1. General Methodology

Descriptive statistics will be displayed for all documented and derived variables. For continuous variables, number of observations, number of missing values, mean, standard deviation, minimum, median and maximum will be calculated. For categorical variables, number of patients, absolute and relative frequencies will be calculated.

In this parallel, controlled study, data analysis will be performed using unadjusted analysis, i.e. simple paired and unpaired t-test under the assumption of a normal distribution for the difference of interest.

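### Twelve-month results rest on the earlier recruits alone with no longitudinal model fixed for them, and the last-visit laboratory summary mixes week 26 with week 52

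*SAP*

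**What the plan says.** **Follow-up.** Section 1.2 gives a target ("We aimed to include 80 patients with CKD stages 3a or 3b"), says it was missed, and continues: "Therefore the recruitment got stopped by 31.12.2022". It then notes that a "certain number of patients had only FU visits till 26 weeks post procedure". The last footnote to the flow sheet in Section 1.3 gives the rule: patients who would not reach the 12-month visit by June 2023 "will have a shorter follow up period of 6 months only".

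**Endpoints.** Section 1.1.2 keeps "Change in systolic 24-h ambulatory BP at 3 and 12 months post-procedure from pre-procedure" as a secondary endpoint, and most other blood pressure endpoints are listed at 3, 6 and 12 months together. The closing paragraph of Section 1.1.3 asks for each of these visits to be compared with the pre-procedure value within each arm (paired) and between arms.

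**Method.** Section 2.4 names a linear mixed model for the 6-month primary endpoint. For secondary and observational endpoints it names only a modelling approach that adjusts for baseline imbalance. It gives no visit term, arm-by-visit term or covariance structure. Section 2.9.1 says the data will be analysed unadjusted, by "simple paired and unpaired t-test under the assumption of a normal distribution for the difference of interest", and Section 2.9.4.1 gives an unpaired t-test for the primary endpoint.

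**Missing outcomes.** A patient needs only one post-procedure measurement to be in the ITT population (Section 2.3), so truncated patients belong to it. Section 2.7.1 deals with blank fields, partial dates and withdrawn consent, but not with an absent week-52 outcome.

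**Laboratory values.** Section 2.2 summarises them at baseline, at last visit and "by changes from baseline to last visit for laboratory values". Separately, Sections 1.1.2 and 2.1 analyse creatinine, cystatin C and eGFR at all time points.

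**The concern.** The SAP is dated 01.09.2023, after the June 2023 cut-off, so the truncation was a known feature of the data when the analysis was fixed. The 12-month column of every table will nonetheless come from a smaller and earlier set of patients than the 3- and 6-month columns, and no method is settled that takes this into account.

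Two things are at stake. First, if Section 2.9.1 governs, a 12-month t-test ignores the 3- and 6-month values of truncated patients, although these are likely to be correlated with the value that is absent. Second, a reader who looks across the columns for durability compares different patients. The within-arm paired changes are the more exposed. A cohort difference in mean change that both arms share cancels in the between-arm contrast, but goes straight into a within-arm change.

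The last-visit laboratory summary has a similar fault: it averages half-year with full-year change.

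**Working it through.** The SAP states no final number randomised, number truncated, SD, effect size or correlation, so there is no figure of its own to reproduce. The only randomised count is 20, for the two-centre cohort in Section 2.4. Everything below except the dates rests on assumed inputs.

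**1. Who has week 52.** Counting 52 weeks back from 1 June and 30 June 2023 gives procedure dates of 2 June and 1 July 2022. Recruitment ran to 31 December 2022. The 12-month set is therefore the patients treated up to about mid-2022.

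**2. Precision forgone at 12 months.** Let *f* be the share with week 52 and *r* the correlation between 6- and 12-month change. With monotone missingness in large samples, using the month-6 value multiplies the variance of the 12-month mean, relative to completers only, by 1 − r²(1 − f).

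| r | f | Variance factor | SE factor |
|---|---|---|---|
| 0.5 | 0.8 | 1 − 0.25 × 0.2 = 0.950 | 0.975 |
| 0.7 | 0.4 | 1 − 0.49 × 0.6 = 0.706 | 0.840 |

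Intervals would be about 3% to 16% narrower.

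With both weeks 12 and 26 used and a common correlation ρ, r² is replaced by R² = 2ρ²/(1 + ρ). This is 0.14, 0.33 and 0.58 for ρ = 0.3, 0.5 and 0.7. For a truncated share *t* = 1 − f of 15% to 45%, the variance falls by R² × t, that is, by 2% to 26%.

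As an illustration take N = 40, SD 12 mmHg and t = 30%:
- Completers only: SE = 12 × √(4/28) = 4.54 mmHg.
- Model with ρ = 0.5: 4.54 × √(1 − 0.33 × 0.30) = 4.30 mmHg.
- Nobody truncated: 12 × √(4/40) = 3.79 mmHg.

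The model recovers part of the loss, not all of it.

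**3. Month 6 in all patients against month 12 in early patients.** Suppose the effect is constant over time but differs by cohort, E in early and L in late recruits. Month 6 estimates (1 − t)E + tL and month 12 estimates E. The apparent change is t(E − L). For E = 8 and L = 2 mmHg:
- t = 15%: 0.15 × 6 = 0.9 mmHg
- t = 30%: 0.30 × 6 = 1.8 mmHg
- t = 45%: 0.45 × 6 = 2.7 mmHg

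A simulation (N = 40, SD 12, ρ = 0.5, 4,000 runs) gave 0.9, 1.8 and 2.9 mmHg. With E = 4 and L = 10 the sign reverses; with E = L the shift is zero. In every scenario the 12-month arm difference stayed centred on the early-cohort effect. Comparing months 6 and 12 within the week-52 patients removed the shift to within simulation noise (at most 0.2 mmHg).

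**4. Laboratory change to last visit.** eGFR serves as the worked case because a linear decline is easy to follow. For a decline of *s* per year, the pooled mean change is −s(1 − 0.5t). With s = 3 mL/min/1.73 m² this is −2.78, −2.55 and −2.33 at t = 15%, 30% and 45%, against −1.5 at week 26 and −3.0 at week 52. The summary describes neither time point. If the truncated share differed between arms by 10 to 20 percentage points, the false arm difference would be 0.5 × 3 × 0.10 = 0.15 to 0.5 × 3 × 0.20 = 0.30.

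**The case against.** The strongest reply is that little here is an error.

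- **Section 2.4 may override the t-tests.** It promises a model for all secondary endpoints, and the explicit t-test in Section 2.9.4.1 covers only month 6. This stands in part: completers-only testing at month 12 is one reading, not the only one. But the model in Section 2.4 has no visit structure, and Section 2.9.1 contradicts it, so no longitudinal analysis is fixed on either reading.
- **No 6-versus-12-month test is planned.** That is correct. The mixing of time with cohort arises when the columns are read side by side, as the endpoint lists invite, and it needs cohorts that differ.
- **A reader might infer that the 12-month comparison is biased.** The documents do not support this. One calendar rule applies to both arms under 1:1 randomisation, so the contrast remains fair for the early cohort.
- **A reader might infer that the 3- and 6-month data go unused.** They do not: month 6 is the primary endpoint and month 3 is secondary. They are merely not borrowed for month 12.
- **A reader might infer that one-year kidney function hangs on the last-visit summary.** It does not, because creatinine, cystatin C and eGFR are analysed at all time points. The pooling matters mainly for other safety analytes, such as potassium, liver enzymes and blood counts. For these, last visit is the only change summary that the SAP names.
- **The gain is modest and rests on assumptions.** This stands. The variance formula is a large-sample result, and an unstructured covariance would use up some of the gain in a small trial.

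The analysis is also declared exploratory and descriptive, and Section 2.9.1 reports numbers observed and missing, so the smaller 12-month sample will be visible.

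**Conclusion.** The point holds as one of precision, interpretation and unsettled method. Twelve-month results come from patients treated up to about mid-2022, and neither Section 2.4 nor Section 2.9.1 fixes a model that uses the other patients' earlier visits.

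The avoidable loss is a 12-month variance factor of about 0.71 to 0.95, for assumed r of 0.5 to 0.7 and f of 0.4 to 0.8. The cohort artefact across time is t(E − L): zero if the cohorts respond alike, and 0.9 to 2.7 mmHg for an assumed 6 mmHg cohort difference with 15% to 45% truncated. The last-visit summary mixes two lengths of follow-up, chiefly for safety analytes other than the renal markers.

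The truncation does not affect the 6-month primary contrast and does not bias the 12-month arm comparison. This is a worthwhile, cheap improvement, not a threat to the main result.

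**What to change.** 1. Reconcile Sections 2.4, 2.9.1 and 2.9.4.1 by naming one repeated-measures mixed model per continuous blood pressure and eGFR outcome. Include all ITT patients, with arm by visit (weeks 12, 26 and 52), baseline value by visit and an unstructured covariance. Name a simpler covariance as fallback if the model does not converge at the small N.
2. State the number with and without week 52 by arm. Show the 3- and 6-month results, between and within arms, also in the patients who have week 52, so that the time course is read in the same people.
3. In Section 2.2, replace laboratory change to last visit with changes at week 26 and at week 52.

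The cost is SAP wording and programming, with no new data. The model assumes that absent values are missing at random. That is plausible for a calendar cut, but would fail if late recruits differed at month 12 in ways that their baseline, 3- and 6-month values do not show. The display in item 2 gives a partial check. Patients lost for other reasons would need a sensitivity analysis.
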